Surveys (e.g., demographic, health behaviors, medical history, dietary intake) will be administered at baseline (initiated < 30 weeks gestation, Study Visit 1) and at follow-up (initiated < 36 weeks gestation, Study Visit 2); see Table 1 for the variables to be assessed and timing of their assessments. PA will be objectively measured at baseline and follow-up with ActiGraph physical activity monitors (PAMs, i.e., the CentrePoint Insight Watch) worn continuously for 7 days on the dominant wrist. Continuous glucose monitors (CGM) will be worn continuously for 7 days on the participants' non-dominant upper arm (posteriorly located) at Study Visits 1 and 2 to assess maternal glycemic profile (i.e., DEXCOM G6 devices, participants will be blinded to their CGM data). Infant outcomes [i.e., weight; length; head, abdominal and upper mid-arm circumferences; and skinfolds at four sites (flank, thigh, triceps, bicep and subscapular skinfolds)]^{18,64} will be assessed by study staff within 4 days of birth (i.e., the optional delivery visit).

Participants will be randomized to the STEP Up intervention or the Next Steps intervention (described in Section R) once they have successfully completed all of the data assessments for Study Visit 1 (described in Section L). Intervention staff will inform the participants of their program assignment (i.e., STEP Up or Next Steps) and schedule the first intervention session. All intervention sessions will be conducted remotely (i.e., via phone and/or video chat).

Study visits will occur either remotely (i.e., via phone and/or video chat) or take place in private rooms at the UT Medical Center [e.g., a private office or exam room in the High

Risk Obstetrical Consultants (HiROC) clinic or Preston Medical Library; and Labor and Delivery or the Mother/Baby Units on 3 West, 3 East, and 4 West for the delivery visit].

F. Incentives

Participants will receive payments in the amount of: \$80 for Study Visit 1, \$100 for Study Visit 2, and \$100 for the delivery visit (i.e., \$280 total). Incentive payments will be Walmart gift cards distributed either in person, by mail, or dropped off at the participants home upon completion of all of the data assessment elements associated with that Visit. If a gift card is sent by mail and not received, a replacement will be dropped off at the participants home.

G. Parking

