Participants will receive vouchers to cover the cost of parking at the Medical Center for any in-person Study activities (described in Sections L, N and O; one voucher will be provided at the delivery visit).

Table 1. Variables to be measured at the study visits.

	Medical Chart	Physician Screen/ Study Visit 1 (≤ 30 weeks)	Study Visit 2 (≤ 36 weeks)	Delivery Visit	3-month Infant Follow up Visit	6-month Infant Follow up Visit	9-month Infant Follow up Visit	1-year Infant Follow up Visit
Demographics								
Age		X						
Race-ethnicity		X						
Working status		X	X		X	X	X	X
SES, Marital status, Insurance status		X				X		
Smoking, Alcohol, Illegal drugs		X						
Sleep		X	X					
Biomedical								
Height	X	X						
Weight (pre-pregnancy, during pregnancy and postpartum)	X	X	X		X	X	X	X
Medical history		X			X	X	X	X
Medication use	X	X	X					
Pregnancy history/outcomes	X				X			

Prior use of and intentions for contraceptives		X	X					
Contraception initiation and use following delivery	X				X	X	X	X
Vaccination (flu and Tdap) perceptions and intentions for vaccination	X	X	X		X	X	X	X
Capillary glucose values (i.e., 7 days of values recorded in purple booklets, for women with GDM only)		X	X					
Continuous Glucose Monitor (i.e., 7 days)		X	X					
Infant Anthropometrics				X (optional)	X	X	X	X
Infant feeding and immunizations					X	X	X	X
Actigraph Physical Activity Monitor		X	X		X	X	X	X
Food Frequency Questionnaire (FFQ)		X	X					

Physical activity questionnaires		X	X		X	X	X	X
Stage of change for Physical Activity		X	X					
Diabetes Risk Perception & Family History of Diabetes		X						
Self-efficacy for Physical Activity		X	X		X	X	X	X
Social support for Physical Activity		X	X		X	X	X	X
Symptoms of Depression		X	X					
Adverse events			X					
Acceptance of interventions			X					

H. Advertising the study

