<https://www.utmedicalcenter.org/medical-care/specialty-practices/university-womens-specialists/>

UT Ob/Gyn Center:

<https://utimobgyncenter.utmck.edu/portal/ut-obgyn-center/default.aspx>

University Midwives:

<https://www.utmedicalcenter.org/medical-care/specialty-practices/university-midwives/>

Women's Care Group:

<https://www.utmedicalcenter.org/medical-care/medical-services/specialty-practices/womens-care-group-knoxville/>

K. Recruitment at HiROC

Study staff will also work with HiROC on study recruitment. HiROC clinic staff (e.g., diabetes educators) will also mention the study to potentially eligible women upon their referral to HiROC for GDM, and those who do not refuse/opt out of receiving more information about the study will be referred to study staff for follow-up. Study staff will pre-screen the medical records and summarize their findings for the physician approvers. Physician approvers will review their findings and the medical records before signing off on the physician approval to contact form; at this point, a Project Wellness study ID number will be assigned. Study staff will follow up with potentially eligible patients by email, telephone and/or text messages to distribute information about the study and evaluate the secondary eligibility criteria. Staff will arrange by telephone, email, and/or text message to connect with eligible and interested women for their Study Visit 1. Study staff will call, email, and/or text the participant to remind her of the scheduled day/time/modality (i.e., remote or in-person at UTMC) of her Study Visit 1.

L. Study Visit 1 (Baseline data assessment, scheduling initiated at after 24 weeks and Study Visit ≤ 30 weeks gestation)

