Study staff will make photocopies of the capillary blood glucose values recorded for HiROC clinical care (i.e., between the first new GDM appointment and the follow-up GDM visit one week later, these are recorded in the HiROC purple self-monitoring booklet distributed to all new GDM patients) to supplement the Study Visit 1 data, for women with GDM only. For all participants, all prepregnancy and pregnancy weights, and height, will be abstracted from the medical records, as will the results of all blood glucose testing during pregnancy.

Participants will not be randomized until all elements of Study Visit 1 have been completed (i.e., surveys and FFQ, PAM, PAM diary log, CGM) and received by study staff. These elements must be completed and received by 30 weeks 6 days gestation in order to be randomized.

M. Randomization

Participants will be randomized to one of the two interventions upon completion of the Study Visit 1 data assessment; they will be contacted by text message and/or ultimately by telephone, by their interventionist, to learn the group they are assigned to and

schedule the initial intervention session (described below). We plan to recruit and enroll up to 48 participants so that we may randomize at least up to 36. Randomization will be stratified for at risk for GDM vs. diagnosed with GDM (split evenly between strata). We will utilize block randomization (to ensure equal sample sizes), with a block size of 4. The allocation sequence will be managed by [name] (UTK, Public Health) and concealed from the study intervention staff until it is needed. Intervention staff will contact the participants to inform them of their assigned intervention condition and schedule the initial intervention session (at < 31 weeks 6 days gestation).

N. Study Visit 2 (Follow-up Data Assessment, Study Visit ≤ 36 weeks gestation)

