Due to COVID-19, the Delivery Visit may potentially be canceled.

P. Interventions

The primary goal of the PA intervention is to achieve at least 30 minutes per day of walking/stepping in place. The secondary goal is to use a physical activity tracker to log and track their walking/stepping in place, and to get at least 3,000 steps during their 30 minutes of walking/stepping. The STEP Up intervention will offer a FitBit Charge 3; the devices will be managed by Fitabase so that both the participant and the interventionists will be able to view her Activity Log (i.e., the Fitbit's record of minutes spent walking/stepping and the number of steps obtained during those minutes), and will thus encourage the use of that device. Women randomized to the PA intervention will have an initial video chat (i.e., Zoom) counseling session to discuss exercising safely and exercising safely during pregnancy, go over the STEP Up program goals, set a walking/stepping goal for the following week, and receive and review use of the Fitbit to track progress towards their goal. They will then participate in 4 telephone/video chat sessions to discuss progress towards their walking/stepping goals and receive behavior change counseling to maintain and increase their walking/stepping (i.e., approximately 1 telephone session per week). They will be offered optional maintenance sessions

through delivery, as requested (i.e., approximately weekly). If the participant does not have internet access, the intervention will be delivered entirely by telephone.

Women randomized to the 'Next Steps' intervention will receive information on mom and baby wellness that is unrelated to physical activity, diet, metabolism, or weight (e.g., her own immunization status during pregnancy and encouragement to immunize her baby on schedule, infant car seats & safety checks, contraceptive options and a contraceptive plan), delivered in 5 telephone/video chat sessions (identical to the STEP Up intervention described above) in order to control for contact time. As such, the trial is called Project Wellness and it will be advertised that all study participants will work with a lifestyle coach on wellness.

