For both interventions, study staff will schedule the initial intervention session by phone/email/text message. The first session will be by video chat (i.e., Zoom), if possible, and occur at \leq 31 weeks 6 days gestation; and the remaining 4 telephone/video chat sessions are to be completed by \leq 36 weeks 6 days gestation. The first session will last approximately 30-40 minutes. The remaining sessions will be approximately 10-20 minutes in length. Participants in the PA intervention will be given the option to continue their weekly sessions beyond 36 weeks of gestation (i.e., maintenance phase of the intervention, receiving approximately 1 telephone session per week). A subset of intervention sessions will be audio recorded to assess fidelity.

For both interventions, participants will receive an intervention workbook (i.e., specific to Next Steps and STEP up programs), with information organized by session. Intervention staff will offer to send pdfs of the individual sessions' materials via email to those who prefer it.

Given the participants' busy lives, missed intervention sessions are inevitable. For both interventions, after 2 unsuccessful contact attempts to reschedule an intervention session (i.e., participant doesn't call back or send an email/text message with a time to reschedule the session), intervention staff will contact the alternate contact(s) (i.e.,

husband, family member) the participant provided on her baseline Project Wellness survey. Staff will inform the contact person that the participant missed a scheduled phone call/visit and to request she call the staff member back (or send a text) to reschedule the call. These individuals will be contacted only once. After two consecutive weeks of unsuccessful attempts to contact (i.e., with no response by telephone, email or text messaging from the participant or the alternative contact), the participant will be considered a passive drop and will be sent a “passive drop” email (stating she will be dropped from the STEP Up/Next Steps program if she doesn’t reply in 2 days) as a final attempt to reengage her in the intervention.

References

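### Does Study Visit 2 need an earliest date so that the activity and glucose wear cannot begin before the five core sessions are delivered?

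*Protocol*

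**What the plan says.** The follow-up window appears in three places, each time with an upper limit only. Section E has surveys "at follow-up (initiated < 36 weeks gestation, Study Visit 2"; the column heading of Table 1 reads "Study Visit 2 (≤ 36 weeks", and the Section N heading uses the same limit as Table 1. Section L has the woman book Visit 2 when Visit 1 concludes.

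Randomisation comes later. On the Visit 1 materials, Section L states: "These elements must be completed and received by 30 weeks 6 days gestation in order to be randomized". Section M then has intervention staff "inform them of their assigned intervention condition and schedule the initial intervention session (at < 31 weeks 6 days gestation", while Section P allows the first session up to and including 31w6d. On the other sessions, Section P says "the remaining 4 telephone/video chat sessions are to be completed by" 36w6d, at roughly one a week. The comparison programme has the same number and form of sessions, "identical to the STEP Up intervention described above) in order to control for contact time".

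The activity and glucose monitors are each worn for 7 days from Visit 2, and Table 1 places "Acceptance of interventions" at that visit alone. The only stated link between Visit 2 and the sessions is in Section N: a session may be used to remind the woman of her visit. The SAP specifies intention-to-treat analysis, with device measures modelled by observation day and study visit.

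**The concern.** Put side by side, the windows do not line up. On the literal readings the last permitted Visit 2 start is 35w6d (Section E) or 36w0d (Table 1 and Section N). That is 7 or 6 days before the last date for finishing the core sessions. With no earliest date, and with booking done before session 1 has been arranged, nothing in writing stops the wear week from starting after two or three sessions.

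If that happened often, the follow-up measurement would mix women with different exposure to the programme. The group difference in activity or glucose could be smaller than it would be after all five sessions, and the acceptability rating would sometimes describe a half-delivered programme. In a feasibility pilot, a small difference would then be hard to read: a weak intervention, or one measured early. The first-session limit is also written in two ways.

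**Working it through.** The question is one of dates. The documents give no effect size or SD against which to cost dilution.

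**Inputs.** Materials deadline 30w6d (Section L). Latest session 1: 31w6d (Section P) or 31w5d (Section M, strict inequality). Weekly pace, so session 5 = session 1 + 28 days (Section P). Core-session limit 36w6d (Section P). Last Visit 2 start: 35w6d (Section E), 36w0d (Table 1 and Section N, literal), or 36w6d if 36 weeks means 36 completed weeks.

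**Step 1: the latest permitted starter.** The three figures in rows 3 and 5 are for a last Visit 2 start of 35w6d / 36w0d / 36w6d.

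| | Section P limit | Section M limit |
|---|---|---|
| Session 1 | 31w6d | 31w5d |
| Session 5, weekly | 35w6d | 35w5d |
| Last Visit 2 start minus session 5 (days) | 0 / 1 / 7 | 1 / 2 / 8 |
| Session 5 after one slipped week | 36w6d | 36w5d |
| Slipped session 5 minus last Visit 2 start (days) | 7 / 6 / 0 | 6 / 5 / -1 |

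At the stated pace session 5 is never later than the last permitted Visit 2. One slipped week forces overlap on the first two readings and not on the third. A woman who starts a week earlier (session 1 at 30w6d, session 5 at 34w6d) can slip a week and still finish by 35w6d; she needs two slips to reach 36w6d.

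**Step 2: what is permitted, though not forced.** For the latest starter, a Visit 2 at 33w0d, 34w0d or 35w0d follows 2, 3 or 4 sessions. By the last wear day (start + 6 days: 33w6d, 34w6d, 35w6d) the counts are 3, 4 and 5. Both session 1 limits give the same counts. If her sessions were instead spread evenly to the deadline, the interval is 35 / 4 = 8.75 days. At 36w0d, 29 days after session 1, she has had 4 of 5.

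**Step 3: effect on the comparison.** Core session number and schedule are the same in both arms. Visit 2 is booked before the arm is known, so the booked date cannot depend on allocation. Uneven exposure at follow-up can therefore shrink the contrast but does not tilt it. If a fraction p of women were measured early and showed a fraction r of the full effect, the expected contrast would be multiplied by 1 - p(1 - r). The documents give neither p nor r.

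**Step 4: what an earliest date would do.** Suppose wear could not begin before the planned session 5 date. Permitted start days for the latest starter = last start - planned session 5 + 1:

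- Section P limit: 1, 2 or 8 days.
- Section M limit: 2, 3 or 9 days.

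A date fixed at randomisation does not move when a session is missed, so the slipped-week overlap in Step 1 remains. Gestational age at follow-up would still vary. Assuming Visit 1 at 24w0d, 7 days of wear and session 1 at 25w0d, session 5 falls at 29w0d; 35w6d - 29w0d = 48 days, about 7 weeks. That is an upper figure, because Section L has "scheduling initiated at after 24 weeks and Study Visit ≤ 30 weeks gestation" and randomisation also waits for the materials to come back.

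**The case for a change.** The best case for a change is that Visit 2 carries the activity and glycaemic hypotheses and the only acceptability rating, that Section P itself expects missed sessions, and that a timing rule costs a sentence. Overlap is also not confined to the single latest starter: two slipped weeks from 30w6d, or a pace a little slower than weekly, have the same effect. Rating acceptance at Visit 2 suggests that follow-up was meant to come after most sessions, yet no sentence secures it.

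Much of this stands as description. No lower limit is written, the windows differ between sections, and a reader of the results will want to know how many sessions women had received. It does not amount to a defect in the plan. The same features that suggest a late follow-up (the acceptability rating, reminders given during sessions, a maintenance phase described as running beyond 36 weeks) are what staff would go by when booking, and they point to a visit near the end of the window. A Visit 2 at 33 weeks for a woman who began at 31w6d is permitted, but nothing in the documents makes it likely.

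Nor is measurement during the programme wrong in itself. The physical activity arm sets a walking goal at the first session and may continue optional weekly sessions through delivery, and the aim is activity during pregnancy and third-trimester glycaemia.

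**Conclusion.** No change to the plan follows. The missing rule is a gap that staff and analysts can fill sensibly. Following the protocol as written still gives a sound intention-to-treat comparison, and at a weekly pace all five sessions fit before the last permitted Visit 2 on every reading. Adjusting the models for sessions received would condition on something that happens after randomisation, and is not needed. An earliest-date rule is a debatable trade: it buys more uniform exposure for some women, but leaves the latest starters 1 to 3 start days on the literal readings, with a risk of lost follow-up among about 36 randomised women. The slipped-week overlap and most of the spread in gestational age would remain.

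The differences between strict and non-strict limits (Section E against Table 1 and Section N for Visit 2; Section M against Section P for session 1) are worth one day each and are clerical. Those passages need reconciling as housekeeping; which limit is right is for the investigators. A by-arm count of core sessions completed at wear start can be given when the results are described, provided session dates are logged.

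This conclusion rests on three assumptions: sessions run at about the stated weekly pace, Visit 2 is normally held late in its window, and rebooked visits do not depend on the arm. The documents do not say how many women start late, so the size of any dilution is unknown.

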**Statistical Analysis Plan date:**

8/8/2023

Analyses will be intention to treat. Mean daily minutes spent in walk/run activity and MVPA (i.e., device-based measures), as well as mean MET hours per week in the sports and exercise domain overall and just walking and jogging (i.e., questionnaire-based measures) will be compared between groups with Proc Mixed in SAS 9.4. All models will be adjusted for GGI vs. GDM status. Models of the device-based measures will include repeated statements for observation day number, by study visit. The model for total MVPA will include additional adjustment for device wear-time (i.e., by day and study visit). Models for the questionnaire-based measures will include repeated statements for study visit. For the neonatal outcomes, PA intervention verse control group differences will be examined in Proc Mixed, adjusting for GGI vs. GDM status.

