To conduct a pilot feasibility RCT among up to 48 women, either diagnosed with GDM and referred to the High Risk Obstetric Consultants (HiROC) at the University of Tennessee Medical Center Knoxville (UTMC), or at risk for GDM (e.g., failed the 50g, 1-hr screening test) and managed by one of the clinics listed in Section J. The RCT will compare a physical activity (behavior change) intervention (i.e., walking/stepping in place) versus a general wellness intervention (i.e., health education focusing on immunizations, contraceptive options following delivery, etc.) on PA levels, maternal glycemic profile in the third trimester, and infant size and anthropometrics (i.e., weight, length, head, abdominal and upper mid-arm circumference, and skinfolds at the flank, thigh, triceps, bicep and subscapular).

It is hypothesized that the PA intervention will increase PA levels during pregnancy, and improve maternal glycemic profile in the third trimester and infant anthropometric measures at birth. The exploratory hypothesis is that improvements in third trimester glycemic profile mediate the effect of pregnancy PA on the infant anthropometric measures.

C. Study Staff

Student research assistants working on the study (i.e., recruitment, conducting intervention sessions and data assessment visits) will be trained and overseen by Drs. [name] and [name]. All will remain up to date on required IRB trainings and approvals (e.g., CITI trainings and UTMC outside learner approval) for the duration of their work on the study.

D. Usual Care

Usual care at HiROC for women with GDM includes bimonthly to weekly in-person appointments, depending on the patients' needs and adherence to the diabetes

educators' recommendations, to monitor their capillary glucose levels, provide counseling on diet, and prescribe or adjust medications, as needed. PA is usually encouraged at the first GDM appointment, but is not directly prescribed, further discussed or typically tracked in conjunction with usual clinical care. Women at risk for GDM (i.e., who fail the screening but not the diagnostic test), are not seen by HiROC for diabetes education.

E. Data Assessment Overview: The Project Wellness Study Visits

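### The physical activity models do not name the contrast that is the treatment effect; the Visit 2 difference adjusted for the Visit 1 value would sharpen them with data already required

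*SAP*

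**What the plan says.** The SAP's single analysis paragraph lists two device-based and two questionnaire-based PA outcomes, which "will be compared between groups with Proc Mixed in SAS 9.4".

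- **Adjustment:** "All models will be adjusted for GGI vs. GDM status". Total MVPA is also adjusted for wear-time. No other covariate is named.
- **Questionnaire outcomes:** "Models for the questionnaire-based measures will include repeated statements for study visit".
- **Device outcomes:** "Models of the device-based measures will include repeated statements for observation day number, by study visit". This probably puts both visits in one model, but its closing words could also mean a separate model for each visit.

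The protocol has no analysis section that adds to this. Its Aim (Section B) states: "It is hypothesized that the PA intervention will increase PA levels during pregnancy". Section L states: "Participants will not be randomized until all elements of Study Visit 1 have been completed". Section M gives the size: "We plan to recruit and enroll up to 48 participants so that we may randomize at least up to 36". In Table 1 the row "Actigraph Physical Activity Monitor" is marked at Visits 1 and 2 and again at 3, 6, 9 and 12 months, as are the PA questionnaires. The SAP does not say which of these visits enter the models.

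**The concern.** A repeated statement sets the covariance among a woman's rows; it does not define the treatment effect. The hypothesis concerns PA in pregnancy. Visit 1 precedes randomisation, so the arms can differ there only by chance, and Visit 2 is the only pregnancy measurement after randomisation. The natural estimand is therefore the Visit 2 group difference, which the SAP neither names nor excludes.

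At least three two-visit analyses fit the text:

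1. a group coefficient pooled over Visits 1 and 2;
2. a comparison at Visit 2 only;
3. a group-by-visit contrast (difference in change).

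The first averages the Visit 2 effect with a Visit 1 difference whose expectation is zero, so it understates the effect and loses power. The other two are unbiased, but neither uses the Visit 1 value as a covariate. With about 36 women randomised and enrolment capped at 48, precision lost in the analysis cannot be regained by recruiting.

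**Working it through.** **No planned figure to reproduce.** The documents give no effect size, SD, significance level, power target or between-visit correlation for PA.

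**Inputs from the protocol.** Up to 36 randomised in equal groups (Section M), taken as 18 per arm. Visit 1 is complete before randomisation (Section L).

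**Assumptions.** Two-sided 5% test, equal SD (set to 1) of the visit means at both visits, complete data, Visit 1–Visit 2 correlation ρ of 0.4, 0.6 or 0.8, true Visit 2 effect d of 0.8 or 0.5 SD. Power is from the noncentral t with 33 degrees of freedom (32 with the baseline covariate).

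**Standard errors**, with 2/18 = 0.111:

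- Pooled group effect: √(0.111 × (1+ρ)/2), expected estimate d/2
- Visit 2 only: √0.111 = 0.333
- Group-by-visit: √(0.111 × 2(1−ρ))
- Visit 2 adjusted for Visit 1: √(0.111 × (1−ρ²))

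| Analysis | SE at ρ = 0.4 / 0.6 / 0.8 | Power, d = 0.8 | Power, d = 0.5 |
|---|---|---|---|
| Pooled | 0.279 / 0.298 / 0.316 | 29 / 26 / 23% | 14 / 13 / 12% |
| Visit 2 only | 0.333 throughout | 64% | 31% |
| Group-by-visit | 0.365 / 0.298 / 0.211 | 57 / 74 / 96% | 27 / 37 / 63% |
| Visit 2 adjusted for Visit 1 | 0.306 / 0.267 / 0.200 | 72 / 83 / 97% | 36 / 44 / 68% |

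**Simulation** (10,000 trials per setting, stratum in the model). The last row's formula ignores the cost of estimating the baseline slope. Simulated power for the adjusted analysis is 70 / 82 / 97% (d = 0.8) and 34 / 43 / 68% (d = 0.5). The other three rows agree with the table to within about a point at d = 0.8. With no true effect, the pooled test rejects in 5.0 / 4.9 / 5.2% of trials, so type I error is not inflated.

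**Variance ratios for the adjusted analysis.**

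- Against Visit 2 only: 1−ρ² = 0.84 / 0.64 / 0.36. Equivalent size is 36/(1−ρ²), about 43 / 56 / 100 women, before the small cost of the slope.
- Against group-by-visit: (1−ρ²)/(2(1−ρ)) = (1+ρ)/2 = 0.70 / 0.80 / 0.90, below 1 for every ρ below 1 before that cost.

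**Low correlation.** Estimating the slope multiplies the variance by about 32/31. Break-even with Visit 2 only is (1−ρ²) × 32/31 = 1, so ρ² = 1/32 and ρ ≈ 0.18. In simulation at d = 0.8, both analyses have 64.7% power at ρ = 0.2. At ρ = 0, adjustment has 63.3% against 65.0%.

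**Share of the Visit 2 effect recovered by a pooled coefficient.** This is the Visit 2 element of V⁻¹1 divided by 1′V⁻¹1, where V is the two-visit covariance matrix:

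- 0.50 with equal variances and complete data
- 0.34–0.46 if 11–33% of women lack Visit 2 (ρ 0.4–0.8)
- 0.66–0.85 if the Visit 2 SD is 0.8 times baseline, and 0.15–0.34 if 1.25 times (ρ 0.3–0.7)
- 5/6 = 0.83 if all six Table 1 visits entered with equal correlation and a constant effect
- 1.00 with a Visit 2 contrast or visit-specific models

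**The case against.** The SAP paragraph is a short summary, not a list of fixed effects, and a group-by-visit contrast is at least as natural a reading as a pooled group term. On that reading there is no dilution, Visit 1 is used through the within-woman change, and at ρ = 0.8 adjustment gains only about a point of power. This stands as far as it goes: the 0.50 factor and the 23–29% power belong to one reading that the SAP does not state. The six-visit case is weaker still, because Protocol Section E describes PA measurement at baseline and follow-up only and the hypothesis is about pregnancy. But the charitable reading still leaves the contrast unnamed, and baseline adjustment still gains: at ρ = 0.4, 70% against 56% in simulation.

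The correlation is unknown, and the tabulated values all lie above break-even. That is also fair: the gain over Visit 2 alone is conditional on ρ. The downside is under 2 points of power.

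Finally, this is a pilot feasibility trial with no power target, so 0.8 and 0.5 SD are illustrative yardsticks. The SAP nevertheless plans between-group comparisons, and a diluted estimate could mislead planning of a later trial.

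**Conclusion.** The concern holds as a free improvement, not as an error that invalidates the analysis. In the SAP text available for review, no PA contrast and no baseline PA covariate is named, and the permitted analyses can differ in both estimate and precision. At 18 per arm and d = 0.8, simulated power with baseline adjustment is 70 / 82 / 97% at ρ = 0.4 / 0.6 / 0.8. Visit 2 alone gives about 64% and group-by-visit 56 / 74 / 96%. A pooled term, if that is what is fitted, gives 28 / 26 / 23% and about half the effect. These sizes rest on assumed effects and correlations, equal variances and complete data. That the contrast is unnamed, and that Visit 1 is available for every randomised woman, rests on the documents alone. Confidence is moderate, because the intended model may be better than the one described.

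**What to change.** For all four PA outcomes, define the treatment effect as the Visit 2 group difference adjusted for the woman's own Visit 1 value and the GGI/GDM stratum. Either of two models serves:

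- **Baseline-adjusted:** Visit 2 data as outcome (daily values for device measures), with the woman's Visit 1 mean as covariate.
- **Constrained longitudinal:** both visits as outcome with a common baseline mean across arms, reporting the Visit 2 contrast. This also keeps randomised women who lack Visit 2, in line with the intention-to-treat statement.

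State that only Visits 1 and 2 enter and that any postpartum visits are analysed separately. Name the participant as the subject in the repeated structure, so that one woman's days and visits are correlated. Keep the wear-time adjustment for total MVPA.

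The cost is SAP wording, a few lines of code and one degree of freedom, with no new data or visits. The SAP is dated 8/8/2023; if outcome data had been seen before this definition is fixed, label it accordingly.
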